PATIENT CONTROLLED ANALGESIA (PCA) PUMP USAGE: After tDCS administration, patients will be started on a patient controlled analgesia (PCA) pump. For statistical analyses of PCA pump usage, morphine-equivalent analgesic dose will be calculated (e.g., 0.2 mg of hydromorphone = 1.0 mg of morphine). Initial PCA settings will consist of hydromorphone 0.2mg/dose with a lockout interval of 10 minutes. The 4-hour maximum dose will be 4.8mgs with no continuous infusion. If a patient does not tolerate hydromorphone, the PCA medication can be changed to a different opioid and morphine-equivalent dosing will be used. If pain is not adequately controlled, the patient will be reassessed by

study personnel prior to increasing the PCA dosing regimen. PCA pump usage will be downloaded from the PCA pump after discharge from the hospital.

MEDICAL OUTCOMES STUDY SHORT-FORM 36 HEALTH SURVEY (SF-36) is a 36-item measure of general health intended to capture quality of life, functional ability and well-being (mental and physical). The SF-36 will be administered pre-surgery, at discharge, 3-month and 6-month follow-up.

BEST GUESS QUESTIONNAIRE will be used to determine how accurately patients, raters and tDCS operators were able to assess which treatment the patient received. This will assess our success in masking the sham treatments. Any time a guess-confidence rating is greater than 8 (on a 0 to 10 numeric rating scale), the PI will follow-up with the participant and/or administrator in order to determine what factors contributed to this level confidence. If the guess is verified correct by the statistical support personnel and any valid systematic administrative factors are identified (e.g., the participant or tDCS administrator reports that the he/she overheard the device-masking assistant discussing the device configuration, accidentally viewed the randomization codes, or felt/heard some unique tDCS-induced sensations that led them to correctly guess the condition), the participant will remain enrolled in the study (and no feedback will be provided to the administrator or participant regarding whether the guess was correct in order to avoid providing information that may further jeopardize the blind in later subjects). The participant's data will be dropped from analyses and steps will be taken to correct the mask procedure.

Table 1. Overview of the measurement schedule for the proposed study (POD=post-operative day)

Measure	Admission	PACU	POD-0	POD-1	POD-2	Discharge	2-weeks	4-weeks	8-weeks	3 months	6-months
BDI	X					X				X	X
BAI	X					X				X	X
BPI	X					X				X	X
SF36	X					X				X	X
PCA		X	X	X	X						
VAS		X	X	X	X		X	X	X		
MPQ		X	X	X	X		X	X	X		
Pain Diary							X	X	X		
Complications		X	X	X	X	X	X	X	X	X	X
ROM							X	X	X		
LOS						X					

Anesthesia/Surgical Measures and Procedures: Patients must be scheduled to receive unilateral total knee arthroplasty (total knee replacement) or unilateral total hip arthroplasty (total hip replacement) at the Ralph H. Johnson VAMC, to be done either cemented or cementless, either computer-assisted or conventional. The anatomical approach will be decided-upon by the surgeon based on clinical presentation, but procedure type and device manufacturer information will be recorded to permit statistical control for different procedural and device implications on post-operative pain. Preoperatively, patients will receive sedation of up to 2 mg of midazolam and 100 micrograms of fentanyl for their comfort during regional anesthesia block placement. A peripheral femoral nerve block catheter will be placed utilizing sterile technique (chloroprep, sterile glove and drape) and femoral nerve stimulation (< 0.5mA) with or without under ultrasound guidance. A 20 ml bolus of 0.5% ropivacaine will be given through the block needle prior to nerve block catheter placement. The catheter will then be placed at a depth less than 5 cm passed the needle tip and secured to the skin using sterile occlusive dressings. The patient will also receive a single injection sciatic nerve block with a 20 ml bolus of 0.5% ropivacaine utilizing nerve stimulation (< 0.5 mA) with or without ultrasound guidance. Intraoperative management

will be standardized to a general anesthetic with laryngeal mask airway or endotracheal intubation (isoflurane, fentanyl (up to 250 mcg) and succinylcholine or vecuronium). Reversal of neuromuscular blockade will be performed with neostigmine and glycopyrolate as required. Intra-articular injection of local anesthetics or opioids will not be performed in any patient. The patients will be started on the patient controlled analgesia (PCA) pump for pain. The PCA will be discontinued on post-operative day-2 at which time the patient will be transitioned to po pain medications (oxycodone). Surgery and anesthesia duration will be recorded and post-operative care will be standardized among all subjects as per standard VAMC clinical protocols.

tDCS Electrode

Placement: All participants will have an EEG 10-20 cap placed F3 will be marked with a non-toxic felt-tipped pen. The tDCS anode will be placed over the mark (see figure 8) and the cathode will be placed over the right dorsolateral prefrontal cortex (F4). Electrodes will be held in place with Velcro straps.

tDCS Methods: tDCS will be delivered in four 20-minute-sessions (100 minutes total)

[figure not shown]
and will be conducted with the Phoresor-II Auto (Model PM850, Iomed, Salt Lake City Utah, USA) using 2mA current. This constant current device ramps up to the desired amplitude to minimize discomfort for participants and ramps the amplitude back to 0mA at the end of the programmed treatment duration. Electrodes will be standard small (4cm X 4cm) sponge electrodes soaked in a sterile solution of 0.9% sodium chloride insulated by a latex casing. The current density and total charge delivered by the above parameters is consistent with those used safely in the current research literature on tDCS. A very low dose (0.125mL) of topical benzocaine (6%) cream may be applied to the skin beneath the sponge electrodes for ~10 minutes and then removed if the participant experiences strong cutaneous sensations (patient report) during stimulation. After stimulation, a vitamin-E/Aloe cream will be applied to the skin under the electrodes following each treatment to reduce risks associated with skin drying.

tDCS Dosing: Custom-developed software will be used to generate random number sequences and save them in a file-format readable by the tDCS blinding software. Participants will be randomized to one of four groups in order to assess the effects of total tDCS charge on post-operative pain.

Group1 will receive a total of four 20-minute sessions of active 2mA tDCS (2 sessions on post-op day 0; and 2 sessions on post-op day 1)

Group2: will receive a total of two 20-minute sessions of active 2mA tDCS (2 sessions on post-op day 0; and 0 sessions on post-op day1) followed by 2 sessions of sham tDCS (both on post-op day 1).

Figure 8. Trajectory of anodal stimulation associated with the proposed tDCS electrode placement strategy

Group3: will receive a only one 20-minute session of active tDCS on post-op day 0, followed by three sessions of sham tDCS (1 on post-op day 0 and 3 on post-op day 1).

Group4: will receive a total of four 20-minute sessions of sham tDCS (2 sessions on post-op day 0; and 2 sessions on post-op day 1)

This dosing scheme will permit investigators to determine whether more stimulation over time is superior to less stimulation, as well as to determine the efficacy of motor tDCS in the management of perioperative pain.

Blind Maintenance: To ensure blinding, specially-developed software will be utilized to switch the tDCS on and off without any intervention from the patient or experimenters. This will be controlled via a silent solid-state relay driven by an Ontrak ADU218 (Ontario, Canada). For Sham tDCS sessions the stimulator will be turned off following 45s. The initial sham stimulation mimics the transient scalp sensation that is perceived when the stimulator is initially switched on. The order of treatment administration will be encoded in the software so that the administrator only enters a patient number and a session-number to start stimulation without knowing whether those specific numbers are associated with active or sham tDCS. The double-blind may only be broken if the clinical presentation of the patient suggests potential cognitive dysfunction, seizure activity, severe headache or extreme skin irritation under the electrodes.

Procedures and Flow: After determining eligibility and interest, written informed consent will be obtained from participants in the Orthopaedic Surgery Pre-operative clinic. Participants will complete the screening questionnaires and all questions about the study procedures, risks, and benefits will be answered. On the day of surgery, the corresponding Admission questionnaires will be completed. After surgery, participants will be transferred to the post-anesthesia care unit (PACU), awakened, and be hooked-up to standard clinical physiological monitors. Patients will be started on a PCA pump. Pain/mood ratings will be collected and the EEG 10-20 caps will be placed. The anode and cathode placement positions will be marked and the caps will be removed. Sponge electrodes will be soaked in saline, affixed in their rubber electrode casings, attached to the tDCS machine, placed on the scalp, and held in place with Velcro straps. The participant's study ID number and tDCS session number will be entered into the tDCS controller software, linked to the randomization file, and the stimulation session will begin (double-blind). After 20-minutes, the electrodes will be removed and pain/mood ratings will be collected again. Four hours later, the tDCS procedures will be repeated in the participants' hospital room. On post-op day-1, two tDCS sessions will be conducted separated by at least 3 hours. Pain and mood ratings will be collected before and after each tDCS session. Range of motion measurements will be collected before and after each physical therapy session. On the day of discharge, participants will complete the Discharge questionnaire packet. Total length of stay, and post-surgical complications will be recorded. At all follow-up time-points, participants will complete the corresponding measures and opioid use status will be tracked via patient report and verified via chart review.

Statistical Analysis and Power: The orthopaedic surgeons at the Ralph H. Johnson VAMC conduct ~100 unilateral total knee arthroplasties and ~50 unilateral total hip arthroplasties each year . Thus, in order to meet the proposed n-size of the current study, 24 (out of 100) participants will need to be eligible and interested in participating in the trial each year. We will over recruit to permit for drop-outs and participants lost to follow-up. For analysis of primary outcomes associated with Aim-1, participants receiving any active tDCS (groups 1,2 & 3) will be collapsed and compared to the sham-only group. Multivariate multiple regression will be used with group-assignment entered into the model as a binary predictor. Surgery and anesthesia duration, depression & anxiety scores, sex, age, pre-tDCS pain, (ROM) Means and pre-op chronic opioid status will be entered into the model as covariates to permit for statistical control of these potentially confounding variables. Overall differences between real and

sham tDCS groups will then be examined for our primary outcomes: total post-op PCA morphine-equivalent dose, VAS pain-on-average ratings, and mean number of post-operative complications. Using the most conservative effect-size estimate from our series of pilot studies ($d=.70$), with 90 patients in the active tDCS group and 30 in the active-sham group, power is good to detect significant effects if they exist ($\alpha=.016$ (corrected for multiple DV's); $1-\beta >.80$; see figure 9). For Aim-2, MANCOVA will be conducted using all 4 groups and all primary dependent measures in the same model (controlling for surgery and anesthesia duration, depression & anxiety scores, pre-tDCS pain, physical rehab measures and chronic opioid status). With four groups of 30 patients each, assuming a moderate effect size $f^2(V)=.2$, and alpha of .05, power is good detect significant main effects in the model ($1-\beta >.80$). Secondary analyses will be conducted to evaluate long-term effects of tDCS on pain, functioning and quality of life (i.e., 2-wk, 4-wk, 8-wk, 3-month and 6 month-follow-up).

Problems/Challenges/Potential Pitfalls: The proposed tDCS device is an FDA-approved iontophoresis device, and its use for tDCS applications is off-label. The tDCS procedure is minimal-risk and FDA-

approval for tDCS applications using this device is not necessary. The PI has received MUSC IRB-approval for conducting tDCS in the perioperative setting and thus there are limited concerns about receiving approval to conduct the proposed research at the Ralph H. Johnson VAMC.

[figure not shown]
Competing Trials Locally or Nationally and Distinction:

The PI has an ongoing NIH-funded clinical trial of tDCS for post-operative pain at MUSC. However, that trial is focused on optimal cortical targets for stimulation (not dosing) and does not involve the veteran population. The proposed study will be on veterans and will focus on dose-dependent effects of tDCS on post-operative pain and post-surgical recovery.

Impact on Clinical Practice and Future Studies: If positive, this high-quality clinical trial could shift the paradigm of post-operative pain management to take advantage of recent neuroscience developments. Findings from this study will be used to evaluate the necessity for a multi-site clinical trial, and to develop future cross-surgical-specialty studies.

This study will be the first randomized, double-blind, controlled study of tDCS technology as an adjunctive pain management strategy for post-operative pain. Data from this trial will likely yield information regarding the feasibility and efficacy of tDCS as a post-operative pain-management approach. If the proposed pilot trial suggests significant and meaningful effects of tDCS as an adjunctive post-operative pain management strategy, this might change the way post-operative pain management is approached in the future. Findings from this study will be used to evaluate the necessity for an even larger-scale, multi-site clinical trial of the technique, and to determine whether future investigations of tDCS across different surgical specialties might be warranted.

Figure 9. Power by sample-size for primary aim of the proposed study (Aim-1 target n-size = 90 patients)

E. PROTECTION OF HUMAN SUBJECTS

E.1. Risks to subjects

Human Subjects Involvement and Characteristics

Subjects will be 120 patients undergoing TKA and THA surgery at the Ralph H. Johnson VAMC.

Inclusion/Exclusion Criteria

- 1) Between the ages of 25 and 90
- 2) No implanted medical devices above the waist
- 3) Mentally capable of reading, writing, giving consent, and following instructions
- 4) Not pregnant
- 5) Cleared for and scheduled for TKA or THA surgery
- 6) No history of seizures
- 7) Not allergic to latex rubber

Sources of Material

Participants will be enrolled in the study during their hospital stay for TKA or THA and for the following 6 month follow-up period. Data will be psychosocial, pain and behavioral ratings, medical surgical outcomes and PCA opioid use. All data will be collected by the study investigators, clinicians and the research team.

Potential Risks

The risks associated with tDCS are minimal. There is no documented risk of seizure associated with tDCS, but participants with a history of seizure disorder will be excluded to ensure optimum safety. Side effects associated with tDCS include mild headache, tingling, itching, or stinging under the electrodes, and skin irritation. The effect-size of tDCS for post-operative pain appears to be moderate and therefore does not eliminate pain entirely. Nonetheless, if a participant experiences total analgesia via tDCS (which is believed to be an extremely unlikely occurrence as it has never been reported in any of the 1000+ participants who have received tDCS for pain control around the world), it is possible that they might not receive signals indicating over-extension or over-use of their knee(s) after surgery and might incur damage in the joint(s).

Safety in case of pregnancy:

Pregnant women will be excluded from the proposed research.

Risks regarding Confidentiality

Despite efforts to maintain subjects' anonymity and confidentiality, there is always some minimal risk of people other than the study investigators gaining access to subjects' information. Every effort will be made to ensure that subject information will be collected and stored in a manner that ensures the highest level of protection of confidentiality.

E.2. Adequacy of Procedures for Protecting and Minimizing Risk:

Recruitment and Informed Consent

Patients scheduled to undergo TKA or THA surgery at the Ralph H. Johnson VAMC will be recruited during their pre-operative visit in the Orthopedic Surgery Clinic. A letter of invitation will be mailed to perspective participants whom medical staff on the study feel may be eligible to participate in the approved research. These prospective subjects that will receive letters will be identified through clinic referrals from the Ralph H. Johnson VA in Charleston, Sc. A HIPAA waiver of authorization will be on file with the IRB giving the research team permission send IRB approved generic letters of invitation to perspective participants. Written-informed consent will be obtained during this pre-op visit.

Protection against Risks

There are 3 areas in which safeguards to protect subjects from undue risk require discussion. These include the procedures used to obtain informed consent, the procedures used to ensure confidentiality of the subjects' data, and the procedures used to minimize possible risks associated with the laboratory procedures.

Informed Consent. In the consent forms and discussions with an investigator, subjects are advised fully of the procedures to be used, the amount of time required of them, the research procedures that will be conducted, the possible risks and benefits of the procedures, their right to refuse participation in the study without prejudice, their right to terminate participation at any moment without prejudice, and the name and telephone number of the Principal Investigator. All subjects will be required to have capacity to consent.

Confidentiality of Subjects' Responses. In the informed consent form, subjects are told that the information they provide and all findings will be kept strictly confidential, with access limited to the research staff and the possible exception of state or federal regulatory personnel. No one but the project staff has access to the master list linking subjects' names to code numbers, and all information obtained is coded. The respective master lists are kept under strict lock and key.

Research Procedures. We have described above the potential risks of the research procedures. If the subject shows deterioration in their clinical status, we will stop him/her from proceeding in the study, and coordinate appropriate care with a physician at the Ralph H. Johnson VAMC.

Participation in the study will be treated as confidential, as will all records. We will protect the identity of our subjects by keeping the data in file cabinets in the PI's locked office, to which only they have a key and by storing electronic data on secure servers designed for use and access by Brain Stimulation Lab members only.

Data and Safety Monitoring Board. [name] will choose a group of faculty at the VAMC to monitor the data on a bi-annual basis with respect to subject safety issues throughout the award period.

E.3. Potential benefits of the proposed research to the subjects and others

Participants will receive little clinical benefit from participating in the study although if they are randomized to a real tDCS group, there is a chance that they will experience less pain than if they had been randomized to a sham group.

E.4. Importance of the knowledge to be gained

The proper control of acute and chronic pain is one of the most important areas of health care. Despite the profound advances in neuroscience over the past 20 years, we still largely use opiate narcotics for pain control. Total joint replacement procedures involving the knees and hips are some of the most common orthopedic procedures performed. Because the prevalence of arthritis is expected to grow substantially as the population ages, these procedures are likely to become even more common. Adequate postoperative pain control is an important factor in determining recovery time and hospital length of stay. Primary methods used to manage post-operative pain in general involve systemic opioid or other analgesic drug delivery and regional blocks. Despite these pain-management strategies, patients still report considerable post-operative pain, and often struggle to complete post-operative physical therapy regimens. Further, systemic opioid analgesic use, has associated side-effects that can lead to post-operative complications including but not limited to mental-clouding, confusion, respiratory depression, interactions with other medications, addiction in some cases, fatigue, and gastric motility problems. New analgesic strategies are needed that can be used adjunctively to existing strategies with the potential to reduce reliance on opioid analgesia. In two independent pilot studies, the investigators have shown that tDCS can reduce post-operative PCA use by as much as 46% while simultaneously reducing subjective pain ratings. Thus, there appears to be potential analgesic effects of tDCS for post-procedural and post-operative pain. If it proves to be beneficial, this technique could revolutionize current methods for post-operative pain management.

Total Planned Enrollment: 120

TARGETED/PLANNED ENROLLMENT: Number of Subjects			
Ethnic Category	Sex/Gender		
	Females	Males	Total
Hispanic or Latino	4	2	6
Not Hispanic or Latino	66	48	114
Ethnic Category: Total of All Subjects*	120		
Racial Categories			
American Indian/Alaska Native	1	1	2
Asian	4	2	6
Native Hawaiian or Other Pacific Islander	1	1	2
Black or African American	24	16	40
White	40	30	70
Racial Categories: Total of All Subjects*	120		

* The "Ethnic Category: Total of All Subjects" must be equal to the "Racial Categories: Total of All Subjects."

F. REFERENCES/LITERATURE CITATIONS

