- 8) No psychiatric conditions except for depression and/or anxiety disorders as these are commonly seen in patients with chronic pain

Participants will be recruited by members of the research team from the Orthopaedic Surgery pre-operative clinic. Eligible and interested participants will be enrolled in the study during their hospital stay for TKA or THA and for the following 6-month follow-up period. Data will be psychosocial, pain and behavioral ratings, medical surgical outcomes and PCA opioid use. All data will be collected by the study investigators, clinicians and the research team.

Dependent Measures: See table-1 for the schedule of measurement.

THE BECK DEPRESSION INVENTORY (BDI) is a well-researched, brief, self-report depression screening instrument. It consists of 21-items that assess different aspects of depression (e.g., anhedonia, excessive guilt, suicidal ideation, vegetative symptoms, tearfulness).¹⁰³⁻¹⁰⁸ IF ITEM #9 (SUICIDAL IDEATION) IS ENDORSED, PARTICIPANTS WILL UNDERGO A FACE-TO-FACE SELF-SAFETY SCREEN (I.E., INTERVIEW ASSESSING IDEATION, INTENT, PLAN, MEANS) AND A REFERRAL WILL BE MADE TO MENTAL HEALTH SERVICES IF NECESSARY FOR FORMAL EVALUATION AND TREATMENT AS INDICATED.

THE BECK ANXIETY INVENTORY (BAI) is a well-researched, brief self-report anxiety screening instrument. It consists of 21-items that assess different aspects of anxiety experience (e.g., physiological, cognitive, behavioral).¹⁰⁹

THE BRIEF PAIN INVENTORY (BPI) is a 17-item self-report questionnaire designed to assess chronic pain intensity and the impact of pain on general functioning, relationships and mood.^{110, 111}

THE MCGILL PAIN QUESTIONNAIRE (MPQ) is a 21-item self-report scale designed to capture the quality and intensity of the pain experience.^{112, 113} Subjects are asked to place a mark next to appropriate descriptors of their pain. The descriptors are assigned scores and the values load onto 4 factors: 1) Sensory, 2) Affective, 3) Evaluative, and 4) Miscellaneous.

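### High-confidence guesses are checked against the true allocation while the trial is running, and the plan does not keep the principal investigator from inferring the result

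*Combined protocol and SAP*

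**What the plan says.** The procedure is in Section D, Dependent Measures, under the Best Guess Questionnaire. Patients, raters and tDCS operators all guess. The trigger is stated as "Any time a guess-confidence rating is greater than 8 (on a 0 to 10 numeric rating scale), the PI will follow-up with the participant and/or" the administrator, to find out what made the person so sure.

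The consequence has two conditions: "If the guess is verified correct by the statistical support personnel and any valid systematic administrative factors are identified". If both are met, the patient stays enrolled, but "The participant's data will be dropped from analyses and steps will be taken to correct the mask procedure". One safeguard is given: "no feedback will be provided to the administrator or participant regarding whether the guess was correct". Its stated purpose is "in order to avoid providing information that may further jeopardize the blind in later subjects".

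Blind Maintenance, also in Section D, sets a closed list: "The double-blind may only be broken if the clinical presentation of the patient suggests potential cognitive dysfunction", followed by three further clinical presentations (seizure, bad headache, marked skin reaction at the electrodes). Neither section refers to the other.

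Two other statements bear on who could act on knowledge of treatment. Under Participants: "All data will be collected by the study investigators, clinicians and the research team". Under PCA pump usage, a patient with poorly controlled pain is reassessed by "study personnel prior to increasing the PCA dosing regimen".

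**The concern.** The check compares an individual patient's guess with that patient's true allocation, and something visible happens only when the guess is right. The PI holds two of the three pieces of information, namely what was guessed and whether a systematic fault was found. The third, whether the guess was right, can be read from what follows. The no-feedback rule protects two parties and leaves out the person who runs the interview.

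The stake is the blind of the investigator team. Complications and questionnaires are collected to 6 months, and study investigators are among those who collect data. One example the plan gives of a systematic factor is a distinctive sensation from the device. Confirming that a guess based on that sensation was right tells the team which sensation marks real stimulation, and that knowledge carries over to later patients. This would be so even if every patient's data were kept in the analysis.

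**Working it through.** The plan gives no figure for this point, so the check is mainly a comparison of its sections.

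**1. Is the check made mid-trial?** Yes. Withholding feedback to protect later subjects, and then correcting the masking, make sense only while patients are still to be treated.

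**2. Is it on the permitted list?** No. The Blind Maintenance list has four clinical presentations, and a confident guess is not one of them.

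**3. Who is kept from the result?** The administrator and the participant. The PI is not named. No sentence says that the PI is told, and none says that the PI is not.

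**4. What can the PI infer?** The guess format is not given. Assume real versus sham, as in the laboratory pilot (Section C), and suppose the interview has found a fault:

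| Guess | Correction follows | No correction |
|---|---|---|
| real | right: some active tDCS (Group 1, 2 or 3) | wrong: Group 4 |
| sham | right: Group 4 | wrong: some active tDCS |

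Real versus sham is the Aim-1 contrast under Statistical Analysis and Power. If no fault was found, nothing follows either way and nothing can be inferred.

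**5. Whose data are exposed?** Patients in the correction column are dropped under the plan as written. Those in the no-correction column stay in the analysis with a status the PI could infer. In that column the plan also leaves a fault that was actually found uncorrected, because correction depends on the guess being right.

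**6. How many interviews?** Inputs from the Section C laboratory pilot: confidence mean 5.50 (SD 3.10) for real and 4.55 (SD 2.16) for sham. From the power section: 90 active and 30 sham patients. Assume normal ratings, and patient guesses only.

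- Cut at 8: z = (8 − 5.50)/3.10 = 0.81, tail 0.210; z = (8 − 4.55)/2.16 = 1.60, tail 0.055. Patients: 90 × 0.210 + 30 × 0.055 = 18.9 + 1.7 = 20.6.
- Cut at 8.5, for whole-number ratings: z = 3.00/3.10 = 0.97, tail 0.167; z = 3.95/2.16 = 1.83, tail 0.034. Patients: 90 × 0.167 + 30 × 0.034 = 15.0 + 1.0 = 16.0.

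So about 16 to 21 of 120 patients would trigger an interview.

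**7. How many correct guesses among them?** The pilot had 46% correct in the real group and 18% in the sham group. If correctness is unrelated to confidence (an assumption), the count is 18.9 × 0.46 + 1.7 × 0.18 = 9.0, or 15.0 × 0.46 + 1.0 × 0.18 = 7.1. An identified fault is needed as well, so fewer still would lead to a correction.

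**The case against.** A reader might infer that the procedure discloses true arms to the PI. The documents do not support that. Verification belongs to the statistical support personnel, who could apply the exclusion themselves. The PI's knowledge is a possible inference, not a stated step. Nor does a wrong guess always reveal allocation. It does so only where a fault was found, and a correct guess of real leaves three of the four groups open.

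A reader might also infer a threat to the primary outcome through the reassessment before PCA increases. That route is weak. PCA use is downloaded from the pump, the PCA stops on post-operative day 2, and the last tDCS session is on day 1. Guess, interview, verification and disclosure would all have to fit before the pump stops. The questionnaire is absent from Table 1, so early timing cannot be excluded, but in the laboratory pilot guesses were taken at the end. No section says that the PI sets PCA doses, and many later measures are self-reported.

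It can fairly be said that a comparison made by statistical personnel alone does not break the double-blind, a term the plan leaves undefined. That is arguable, and it is why the two sections need aligning. The PI also already knows from the pilot how real and sham sensations differ, so the interview alone adds little. What would be new is confirmation in this trial's patients.

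The count in the working is fragile. It carries one-session ratings from 24 healthy volunteers to surgical patients having four sessions, and it treats Groups 2 and 3, who also receive sham sessions, as fully real. The normal curve also places about 7% of real-group ratings above 10, a third of the 21% tail (0.073/0.210 = 0.35).

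What remains after all this is the mid-trial check itself, the dependence of correction on its result, and the PI's absence from the no-feedback rule.

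**Conclusion.** The concern holds as a gap in protecting the blind. A check against allocation runs during the trial, outside the closed list of reasons for breaking the blind, and its visible consequence could let the PI infer real versus sham status. Actual disclosure is not established. The exposure is mainly to follow-up outcomes in patients who stay in the analysis, and to the masking of later patients.

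The size cannot be estimated reliably. The 16 to 21 figure counts triggered patient interviews, not disclosures, and rests on normality and on the pilot ratings carrying over. Guesses by raters and operators would add to it by an unknown amount. The inference in the working assumes a real-versus-sham question and an identified fault. The change is still worth making because it costs little and also closes the case in which a fault is found but left uncorrected.

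**What to change.** Amend the Best Guess Questionnaire text in three ways:

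- The PI follows up every guess with confidence above 8 in the same way and corrects any masking fault found, whether or not the guess was right.
- The statistical support personnel compare guesses with allocation only after the 6-month database is locked. Until then no result, direct or implied, goes to the PI, raters or operators. Any rule on dropping data that depends on a correct guess can then be applied only after lock.
- Blind Maintenance and the Best Guess Questionnaire refer to each other, so that the list of reasons for breaking the blind and the guess procedure agree. The listed clinical reasons are not affected.

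The cost is protocol wording. The downside is that faults are corrected without knowing whether the guess that brought them to light was right, so some corrections may prove unnecessary. A narrower change, stating only that the PI and raters are not told the result, would be simpler. It would leave correction dependent on verification, and so leave the inference open to anyone who sees whether the masking was changed.
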